9.1.1 Adverse Event

A Vitamin D related adverse event (AE) is defined as any untoward medical occurrence in a subject or clinical investigation subject administered a pharmaceutical product and which possibly has a causal relationship with this treatment. An adverse event can therefore be any unfavorable and unintended sign (including an abnormal laboratory finding), symptom, or disease temporally associated with the use of a medicinal (investigational) product.

A Vitamin D related adverse event can result from use of the drug as stipulated in the protocol or labeling, as well as from accidental or intentional overdose, drug abuse, or drug withdrawal. Any worsening of a pre-existing condition or illness is considered an adverse event if related to Vitamin D. Laboratory abnormalities and changes in vital signs are considered to be adverse events if they result in discontinuation from the study, necessitate therapeutic medical intervention, meet protocol specific criteria and/or if the investigator considers them to be adverse events related to Vitamin D. In general, if a laboratory abnormality or change in vital sign is associated with a specific diagnosis that is being reported concurrently as an adverse event (e.g. elevated creatinine with renal failure) the findings that support the diagnosis do not need to be reported as separate adverse events unless the investigator feels it is appropriate.

9.1.1.1 Treatment-emergent Adverse Event

Treatment-emergent Vitamin D related adverse event is defined as any adverse event with onset or worsening from the time that the first dose of study drug is administered until 30 days after the final dose of study drug is administered.

9.1.1.2 Unexpected Adverse Event

An unexpected Vitamin D related adverse event is any adverse drug event that is not listed in the current labeling/Investigator's Brochure. This includes events that may be symptomatically

and pathophysiologically related to an event listed in the labeling, but differ from the labeled event because of greater severity or specificity. For example, under this definition, hepatic necrosis would be unexpected (by virtue of greater severity) if the labeling only referred to elevated hepatic enzymes or hepatitis. Similarly, cerebral thromboembolism and cerebral vasculitis would be unexpected (by virtue of greater specificity) if the labeling only listed cerebral vascular accidents. “Unexpected,” as used in this definition, refers to an adverse drug experience that has not been previously observed (i.e., included in the labeling) rather than from the perspective of such experience not being anticipated from the pharmacological properties of the pharmaceutical product.

9.1.2 Serious Adverse Event

A Vitamin D related serious adverse event is one that at any dose (including overdose) that:

- Results in death
- Is life-threatening¹
- Requires inpatient hospitalization or prolongation of existing hospitalization
- Results in persistent or significant disability or incapacity²
- Is a congenital anomaly or birth defect
- Is an important medical event³

¹“Life-threatening” means that the subject was at immediate risk of death at the time of the serious adverse event; it does not refer to a serious adverse event that hypothetically might have caused death if it were more severe.

²“Persistent or significant disability or incapacity” means that there is a substantial disruption of a person’s ability to carry out normal life functions.

³Medical and scientific judgment should be exercised in deciding whether expedited reporting is appropriate in situations where none of the outcomes listed above occurred.

Important medical events that may not be immediately life-threatening or result in death or hospitalization but may jeopardize the subject or may require intervention to prevent one of the other outcomes listed in the definition above should also usually be considered serious. Examples of such events include allergic bronchospasm requiring intensive treatment in an emergency room or at home, blood dyscrasias or convulsions that do not result in subject hospitalization, or the development of drug dependency or drug abuse. A new diagnosis of cancer during the course of a treatment should be considered as medically important.

9.2 Adverse Event Reporting Per University of Nebraska Medical Center, IRB and Fred & Pamela Buffett Cancer Center Data and Safety Monitoring Committee (DSMC):

This protocol will adhere to all institutional guidelines for adverse event reporting.

9.2.1 IRB Reporting

All Vitamin D related internal serious adverse events (SAEs) must be reported to the local IRB promptly per institutional human research protection program policies.

9.2.2 Fred & Pamela Buffett Cancer Center Data and Safety Monitoring Committee (DSMC) Reporting

All Vitamin D related adverse events grade 3 or higher (expected or unexpected) will be reported to the University of Nebraska Medical Center, Fred & Pamela Buffett Cancer Center Data and Safety Monitoring Committee (DSMC) in accordance with DSMC guidelines.

In its initial review, the DSMC will make a recommendation for the frequency of DSMC monitoring based on an assessment of risk associated with study-associated therapy, per the DSMC policy.

Detailed policy and procedures for this section may be reviewed at:

<http://www.unmc.edu/cancercenter/clinical/prms.html>

Attribution of AE: The likelihood of relationship of the AE to the study drugs will be determined by the investigator based on the following definitions:

- **Not Related:** The subject was not exposed to the study treatment or another cause is obvious.
- **Probably Not Related:** The AE is most likely explained by another cause, and the time of occurrence of the AE is not reasonably related to the study treatment.
- **Possibly Related:** Study treatment administration and AE occurrence reasonably related in time, and the AE is explained equally well by causes other than study treatment, or treatment administration and AE occurrence are not reasonably related in time, but the AE is not obviously a result of other causes.
- **Probably Related:** Study treatment administration and AE occurrence are reasonably related in time, and the AE is more likely explained by study treatment than by other mechanisms.
- **Definitely Related:** There occurrence and timing of the AE are clearly attributable to the study treatment.

Severity Grade of AE. The severity of events reported on the AE case report form will be determined by the principal investigator according the NCI Common Toxicity Criteria (CTC version 4.0). Copies of the AE report will be submitted to the IRB as indicated in Section 9.1.1.

9.3 Auditing

The UNMC Fred & Pamela Buffett Cancer Center Scientific Review Committee (SRC) will review this protocol on at least an annual basis.

This study will undergo audit on at least a semi-annual basis by the UNMC Fred & Pamela Buffett Cancer Center Audit Committee.

Detailed policy and procedures for this section may be reviewed at:

<http://www.unmc.edu/cancercenter/clinical/prms.html>

Section 10.0 Statistical Considerations:

Primary Objective

To evaluate the **Primary End Point**, the 3 year progression-free survival (PFS), defined as time from the time of study entry of the "watch and wait" or newly diagnosed NHL or CLL until relapse, progression, starting new therapies or death from any cause. Response will be determined by the principal investigator or the lead site investigators. The 3 year PFS of the low dose and high dose groups will each be compared to a historical fixed expected 3-year PFS of 45%.

Secondary Objectives

To evaluate changes in the levels of serum vitamin D levels during therapy with daily oral Vitamin D supplementation.

To evaluate the **Secondary End Point**, the overall survival (OS), defined as defined as time of study entry of "watch and wait" or newly diagnosed NHL or CLL until death from any cause. For subjects who are still alive at the time of the study analysis at 3 years or are lost to follow-up, survival will be censored at the last recorded date that the subject was known to be alive.

Study Endpoints

The **primary end point** is 3 year progression-free survival (PFS), defined as time of study entry of "watch and wait" or diagnosed NHL or CLL until relapse, progression, starting new therapies or death from any cause. Response will be determined by the principal investigator or the lead site investigators.

The **secondary end point** is 3 year overall survival (OS), defined as defined as time of study entry of "watch and wait" or newly diagnosed NHL or CLL administered on trial until death from any cause.

10.1 Patient Accrual

Subjects found to have low levels of serum Vitamin D <30 ng/ml at time of enrollment will be randomized on a 1:1 basis to receive vitamin D 5000 IU daily (Higher Dose Cohort) or vitamin D 1000 IU daily (Lower Dose Cohort) stratified by disease group aggressive NHL (fast-growing tumors) or indolent NHL/CLL (slow-growing tumors).

The sample size calculations are based on the primary endpoint of 3-year PFS. The expected PFS for patients with low levels of serum Vitamin D is 45%.⁴⁴ The 3 year PFS of the low dose and high dose groups will each be compared to a historical fixed expected 3-year PFS of 45%.⁴⁴ The sample size calculations are based on a single arm survival calculation based on an assumption of exponentially distributed PFS times using a 3-year PFS of 60% for each of the randomized arms (low dose or high dose). Therefore, the sample size calculations are based on detecting a 15% difference in 3-year PFS for each randomized arm (low dose or high dose) vs.

a historical fixed expected PFS of 45%. Since such single arm studies are typically conducted as a one-sided test, we use $\alpha = 0.025$, however, no other adjustments will be made for multiplicity. Sample size calculations were conducted using the SWOG statistical calculator found at https://www.swogstat.org/stat/public/one_survival.htm.

Using a one sided test with accrual time of 2 years, follow-up time of 3 years, $\alpha = 0.025$, a null PFS of 45% and an alternative PFS of 60% a total of 230 eligible patients will be enrolled in the normal serum Vitamin D group based on current accrual rate and until 70 eligible patients in each randomized arm (low or high dose) to provide 80% power. These results assume that two sequential tests are made (1 interim analysis and the final analysis) using the O'Brien-Fleming spending function to determine the test boundaries. Our final enrollment is projected to be 370 patients expecting a ~10% loss to follow-up/inevaluability rate.

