2.8 Vitamin D in Non-Hodgkin's Lymphoma

A pooled analysis of 10 studies found that higher levels of recreational sun exposure, which would be anticipated to increase vitamin D levels was associated with a lower risk for non-Hodgkin's lymphoma.⁴⁰ Furthermore, data from 2 prospective cohort studies provide suggestive evidence that low serum 25 (OH) D levels are associated with increased incidence of NHL.^{41,42} There are only a few studies that have evaluated the relationship of vitamin D and non-Hodgkin's lymphoma.³² A study performed by Shanafelt et colleagues (2011) evaluated 390 newly diagnosed CLL patients. The time to treatment (TTT) was HR=1.47; P=.008 and overall survival (OS) was not significant in both cohorts (HR=1.47; P=.07) in the multivariate analysis of the patients adjusting for variables but in the individual cohorts there was a shorter TTT and OS in patients with CLL that were 25 (OH) D insufficient at time of diagnosis.⁴³

Another trial performed by Drake et colleagues (2010) evaluated vitamin D insufficiency and prognosis in non-hodgkin's lymphoma.² Circulating 25-hydroxyvitamin D [25(OH) D] levels were predictive of event-free survival (EFS) and overall survival (OS) in a prospective cohort of 983 newly diagnosed patients with NHL. 25(OH) D and 1, 25-dihydroxyvitamin D [1, 25(OH) 2D] Median follow-up was 34.8 months; 404 events and 193 deaths of which 168 from lymphoma. For DLBCL, 52% of the patients were 25(OH) D insufficient. After adjusting for known prognostic factors and treatment, 25(OH) D insufficient patients with diffuse large B-cell

lymphoma (DLBCL) had inferior (hazard ratio [HR], 1.41; 95% CI, 0.98 to 2.04) and OS (HR, 1.99; 95% CI, 1.27 to 3.13). The association of 25(OH) D levels with EFS and OS was mainly observed over the range of 15 to 25ng/mL, and was relatively flat above 30 ng/mL.²

T-cell lymphoma (which included PTCL and CTCL), 57% of the patients were 25(OH) D insufficient, and after adjustment for known prognostic factors insufficient patients continued to have an inferior EFS (HR, 1.94; 95% CI, 1.04 to 3.61) and OS (HR, 2.38; 95% CI, 1.04 to 5.41). Inferior EFS and OS were observed among TCL patients in both the insufficient (<25 ng/mL) and the lower end of the optimal range (25 to 80 ng/mL) of 25 (OH) D levels. Vitamin D deficiency in mycosis fungoides and Sézary syndrome patients is similar to other cancer patients.²

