The prevalence of 25 (OH) D insufficiency for the remaining subtypes ranged from 27% to 39%, and there were no associations of 25 (OH) D insufficiency with EFS. There were no association with EFS for the other NHL subtypes. Among patients with DLBCL and T-cell lymphoma, higher 1,25 (OH) 2D levels were associated with better EFS and OS, suggesting that any putative tumor 1- α -hydroxylase activity did not explain the 25(OH) D associations. 25 (OH) D insufficiency was associated with inferior EFS and OS in DLBCL and T-cell lymphoma. One potential interpretation of the association of low 25 (OH)D levels with inferior DLBCL and TCL prognosis is that patients with larger tumor burden might have increased conversion of 25 (OH) D to 1,25 (OH)2D due to increased 1- α -hydroxylase activity from the tumor, leading to artificially low serum 25(OH)D levels. This study did not support the hypothesis that the association of lower 25 (OH) D levels were poor prognosis in DLBCL and TCL is confounded by tumor production of 1- α -hydroxylase. Further, these data also indicate that there appears to be a direct association of lower 1, 25 (OH) 2D levels with inferior outcome.²

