Another study that looked at newly diagnosed follicular lymphoma (FL) was SWOG participants that were previously untreated patients with FL enrolled on a clinical trials involving CHOP chemotherapy plus an anti-CD20 antibody (rituximab or iodine-131 tositumomab) between 1998 and 2008 or participants also previously untreated patients with FL enrolled onto the Lymphoma Study Association (LYSA) PRIMA trial of rituximab plus chemotherapy (randomly assigned to rituximab maintenance versus observation) between 2004 and 2007 had 25-hydroxyvitamin D measured at baseline. The primary end point was progression-free survival (PFS). After a median follow-up of 5.4 years, the adjusted PFS and overall survival hazard ratios for the SWOG cohort were 1.97 (95% CI, 1.10 to 3.53) and 4.16 (95% CI, 1.66 to 10.44), respectively, for those who were vitamin D deficient (< 20 ng/mL; 15% of cohort). After a median follow-up of 6.6 years, the adjusted PFS and overall survival hazard ratios for the LYSA cohort were 1.50 (95% CI, 0.93 to 2.42) and 1.92 (95% CI, 0.72 to 5.13), respectively, for those who were vitamin D deficient (< 10 ng/mL; 25% of cohort). Conclusion of this study demonstrated that although statistical significance was not reached in the LYSA cohort, the consistent estimates of association between low vitamin D levels and FL outcomes in two independent cohorts suggests that serum vitamin D might be the first potentially modifiable factor to be associated with FL survival.⁴⁴

We propose to conduct a Pilot study evaluating the effects of vitamin D supplementation on the 3-year PFS and OS of patients with newly diagnosed or previously untreated (patients may be under no treatment “wait and watch” or have received two cycles of chemotherapy before informed consent) Non-Hodgkin’s Lymphoma or CLL.

Section 3.0: Eligibility Criteria:

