10.2.4 Analysis for the Secondary Endpoint

The secondary endpoint of 3-year OS will be analyzed as described for the primary endpoint, using a historical fixed outcome of 80%.⁴⁵

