10.4 Stopping Rules

10.4.1 Interim Analyses

One interim monitoring analysis for efficacy will be conducted after n=35 patients in each randomized arm (35 patients in the low dose group and 35 patients in the high dose group) have enrolled. Two separate tests will be conducted to compare 1- the PFS in the low dose arm to the fixed expected value of 45% and 2- the PFS in the high dose arm to the fixed expected value of 45%. We will use an O'Brien-Fleming-type spending function to assess whether the interim results are sufficient to conclude that vitamin D supplementation in either the low dose or high dose arm is effective in increasing the PFS to 60%. The monitoring boundary p-values associated with the 1 interim look using the O'Brien-Fleming spending function will be 0.001525 with the final analysis being done with p=0.024501. The type I error associated with this monitoring plan is approximately 0.025. If $\geq 10\%$ of patients in either Vitamin D arm has severe adverse events that are felt to be directly related to the Vitamin D supplement, the study will be stopped.

Section 11.0 Records to Be Kept:

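### The 45% null for 3-year PFS is not justified for the randomised population, and a null set only a few points too low lets an inactive supplement be declared effective

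*Combined protocol and SAP*

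**What the plan says.** Section 10.1 sets the benchmark: "The expected PFS for patients with low levels of serum Vitamin D is 45" per cent, with reference 44 as its source. The design is then sized on "a null PFS of 45% and an alternative PFS of 60" per cent, with 70 eligible patients per randomised arm for 80% power at one-sided 0.025. The same figure recurs in 1.1.1, 10.2.3 and 10.4.1.

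Section 10.2.3 tests each dose arm against that single figure with a one-sample log-rank test. The normal-level group appears on the Kaplan-Meier plots, but no efficacy comparison with it is specified. Section 10.4.1 allows either arm to be judged effective at the interim on the same benchmark; the boundary p-value "will be 0.001525 with the final analysis being done with p=0.024501".

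Section 2.8 describes reference 44 as two cohorts of previously untreated follicular lymphoma given chemotherapy plus an anti-CD20 antibody. It reports hazard ratios "for those who were vitamin D deficient (< 20 ng/mL; 15% of cohort") in one cohort and below 10 ng/mL (25%) in the other. No absolute PFS is quoted. The section also describes 983 newly diagnosed NHL patients: "Median follow-up was 34.8 months; 404 events and 193 deaths of which 168 from lymphoma". Outside DLBCL and T-cell lymphoma in that cohort, "there were no associations of 25 (OH) D insufficiency with EFS".

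**The concern.** With a fixed historical null, the null carries the whole inference. The test asks only whether an arm does better than 45%. It cannot separate an effect of vitamin D from a case mix that would have exceeded 45% without it.

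The source differs from this trial in histology, treatment and vitamin D cut-off. Randomisation is stratified by aggressive NHL versus indolent NHL/CLL, groups expected to differ in PFS, yet one number serves both. If the true untreated rate is higher, the per-arm error rate rises well above 2.5%, and no planned analysis would reveal it.

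**Working it through.** **1. The plan's own sample size.** Inputs from 10.1: null 45%, alternative 60%, exponential PFS, 2 years' accrual, 3 years' follow-up, one-sided 0.025.
- λ0 = −ln(0.45)/3 = 0.2662 per year; λ1 = −ln(0.60)/3 = 0.1703 per year.
- Event probability under the alternative: e = 1 − [exp(−3λ1) − exp(−5λ1)]/(2λ1) = 0.491.
- Expected events per patient under the null: E = e·λ0/λ1 = 0.768.
- n = [(z_α√E + z_β√e)/(E − e)]² = [(1.960×0.877 + 0.842×0.701)/0.277]² = 69.5. At the final-analysis level of 0.024501, n = 70.0.

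The 70 per arm reproduces, so any weakness lies in the input and not in the arithmetic.

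**2. Source against trial.**

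| | Source of 45% (Section 2.8) | This trial (3.1, 10.1) |
|---|---|---|
| Disease | Follicular lymphoma | Any NHL or CLL |
| Treatment | All on chemo-immunotherapy | Watch-and-wait, or up to two prior chemotherapy cycles or local radiotherapy; other therapeutic trials allowed |
| Low vitamin D | <20 or <10 ng/mL | <30 ng/mL |
| Strata | – | Aggressive; indolent/CLL; one null for both |

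**3. What the all-NHL cohort suggests.** Crude event-free share: 1 − 404/983 = 58.9%. This ignores censoring, so it is not a 3-year estimate. I assumed follow-up patterns with median 2.9 years (all at 2.9, or uniform over 0–5.8, 1–4.8 or 2–3.8 years) and a constant or falling hazard. The implied 3-year EFS is then about 54.5–58%, still for all vitamin D levels.

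**4. Low-level patients.** Let s be the event-free rate in sufficient patients, w the insufficient share and S the overall rate. Solve (1 − w)s + w·s^HR = S; the insufficient rate is s^HR. Inputs: S = 54.5–58%; w = 27–57% (the cohort's range across subtypes); hazard ratios from Section 2.8.

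| HR applied to every subtype | Where Section 2.8 reports it | 3-year rate, insufficient |
|---|---|---|
| 1 (no association) | Other NHL subtypes | 54.5–58% |
| 1.41 | DLBCL | 46–53% |
| 1.50 | Follicular, second cohort | 44–53% |
| 1.94–1.97 | T-cell; follicular, first cohort | 38–49% |

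The last row needs the largest hazard ratios to hold in every subtype, so I treat it as an extreme. The first three rows span the mid-40s to the high 50s.

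**5. Consequence for the test.** I simulated 100,000 arms of 70 under exponential PFS with no vitamin D effect. The null is rejected when (expected − observed)/√expected exceeds the one-sided critical value at 0.025 or 0.024501. Expected events use λ0. Ranges cover follow-up stopped at 3 years and follow-up of 3–5 years.

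| True untreated 3-year PFS | Declared effective, per arm |
|---|---|
| 45% | about 2% |
| 48% | 6–7% |
| 50% | 11–13% |
| 53% | 24–29% |
| 55% | 35–43% |

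The formula in step 1, rearranged for power with 2 years' accrual, gives 13% at 50% and 42% at 55%, in agreement. With 63 evaluable patients (10% loss) it gives 12% at 50%.

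**The case against.** The strongest reply is that nothing in the documents shows 45% to be wrong. Section 2.8 quotes no absolute PFS from reference 44, and step 4 includes 45%. That stands.

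Three stronger readings are tempting and are not supported:
- **That the protocol's own data give 59% at 3 years, next to the 60% alternative.** The 58.9% ignores censoring, covers all vitamin D levels, and comes from a cohort whose insufficiency cut-off is quoted as below 25 ng/mL. At that rate false success would be 62–71% per arm, but only if low vitamin D had no prognostic effect at all.
- **That any null below about 51% is untenable.** This overlooks censoring and the other hazard ratios in Section 2.8: 1.97 and 1.50 for PFS in follicular lymphoma, and 1.47 for time to treatment in CLL. Starting new therapy is a PFS event in this trial. The documents do not define the cohort's EFS or say that it included CLL or watch-and-wait patients.
- **That the OS benchmark exposes the inconsistency.** Section 10.2.4 tests OS "using a historical fixed outcome of 80" per cent, and the cohort's crude survival is 1 − 193/983 = 80.4%. Nothing links the two: the reference attached to the 80% is the paper on the test method.

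A further objection concerns cost. Replacing the null needs stratum-specific data that the documents lack. If the 60% alternative is kept, the step 1 formula gives 70 per arm about 35% power against a null of 51% and 17% against 54%; 80% power would need roughly 190 and 430 per arm. That is a good reason not to replace the null now. It does not answer the lack of justification. The pilot label does not answer it either, since the plan sets a formal alpha, 80% power and an efficacy boundary.

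**Conclusion.** The point holds in this form: 45% is unjustified for the randomised population, and the primary conclusion for each arm depends on it alone. A null 5 points too low raises the per-arm false-success rate from 2.5% to 11–13%; 8 points gives 24–29% and 10 points gives 35–43%.

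These rates assume exponential PFS, 70 patients per arm, the one-sided level in 10.1 and the final test only. The mid-40s to high-50s range rests on the assumed follow-up patterns, on cohort EFS standing in for this trial's PFS, and on one hazard ratio and insufficient share applied across subtypes. Section 2.8's lack of association outside DLBCL and T-cell lymphoma makes the 50s credible; its follicular and CLL results keep the mid-40s credible. The documents do not settle which is right, so the trial should not claim efficacy on this benchmark alone.

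**What to change.** Keep 45% as the design null and make these additions:
1. In 1.1.1 and 10.1, state that the source of 45% differs from this trial in histology, treatment and vitamin D cut-off.
2. In 10.2.3, pre-specify the one-sample log-rank for each arm over nulls of about 45–60%, and report the highest null each arm rejects.
3. In 10.2.3, add a comparison of each arm with the concurrent normal-level cohort, adjusted for disease group (aggressive; indolent/CLL), as a check on the benchmark. For scale, if that cohort's 3-year PFS were 60%, a 45% rate in untreated low-level patients would need a hazard ratio of ln(0.45)/ln(0.60) = 1.56.
4. In 10.2.3 and 10.4.1, state that exceeding 45% alone will not be reported as evidence that vitamin D is effective.

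No new patients are needed and the sample size is unchanged. The cost is a little more analysis and a weaker permitted claim. The normal-level comparison is non-randomised, and its year-3 window is ±180 days against ±30 days in the randomised arms (Section 7.0). It can support or undermine the benchmark but cannot prove efficacy.
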